#### MEDI4736 and Tremelimumab Fixed Dosing Regimens

A population PK model was developed for MEDI4736 using monotherapy data from the Phase 1 study, CD-ON-MEDI4736-1108 (N = 292; doses of 0.1 to 10 mg/kg Q2W or 15 mg/kg Q3W; solid tumors). Population PK analysis indicated only minor impact of body weight on PK of MEDI4736 (coefficient of  $\leq 0.5$ ). The impact of body weight-based (10 mg/kg Q2W) and fixed dosing (750 mg Q2W) of MEDI4736 was evaluated by comparing predicted steady-state PK concentrations (5th, median and 95th percentiles) using the population PK model. A fixed dose of 750 mg was selected to approximate 10 mg/kg (based on median body weight of ~75 kg). A total of 1000 subjects were simulated using body weight distribution of 40 to 120 kg. Simulation results demonstrate that body weight-based and fixed dosing regimens yield similar median steady-state PK concentrations with slightly less overall between-subject variability with fixed dosing regimen.

Similarly, a population PK model was developed for tremelimumab using data from Phase 1 through Phase 3 (N = 654; doses of 0.01 to 15 mg/kg Q4W or every 90 days; metastatic melanoma; Wang et al, 2014). The population PK model indicated minor impact of body weight on PK of tremelimumab (coefficient of  $\leq$  0.5). The weight-based (1 mg/kg Q4W) and fixed dosing (75 mg/kg Q4W; based on median body weight of ~75 kg) regimens were compared using predicted PK concentrations (5th, median and 95th percentiles) using population PK model in a simulated population of 1,000 subjects with body weight distribution of 40 to 120 kg. Similar to MEDI4736, simulations indicated that both body weight-based and fixed dosing regimens of tremelimumab yield similar median steady state PK concentrations with slightly less between-subject variability with fixed dosing regimen.

Similar findings have been reported by others (Ng et al, 2006; Wang et al, 2009; Zhang et al, 2012; Narwal et al, 2013). Wang and colleagues investigated 12 mAbs and found that fixed and body size-based dosing perform similarly, with fixed dosing being better for 7 of 12 antibodies (Wang et al, 2009). In addition, they investigated 18 therapeutic proteins and peptides and showed that fixed dosing performed better for 12 of 18 in terms of reducing the between-subject variability in PK/pharmacodynamics parameters (Zhang et al, 2012).

A fixed dosing approach is preferred by the prescribing community due to ease of use and

reduced dosing errors. Given expectation of similar PK exposure and variability, we considered it feasible to switch to fixed dosing regimens. Based on an average body weight of 75 kg, a fixed dose of 750 mg Q2W MEDI4736 is equivalent to 10 mg/kg Q2W, 1500 mg Q4W MEDI4736 is equivalent to 20 mg/kg Q4W, and 75 mg Q4W tremelimumab is equivalent to 1 mg/kg Q4W.

#### Dosing schedule for Tremelimumab and Durvalumab

The two drugs will be administered in 3 different arms as per current IB specifications:

#### Treatment Arms:

On all arms, patients will be given the 1st dose(s) of study treatment 14 days pre-surgery. Patients will then undergo standard surgical resection. Dosing will then resume approximately 14 days after surgery (once the surgical wound has healed) and will follow the schedule outlined below (depending on the arm to which they were assigned):

Arm 1) Tremelimumab- 75 mg every 4 weeks. The drug will be restarted 14 days after surgery once the surgical wound has healed and then every 4 weeks after surgery. If there is no progression of disease, they will continue on treatment for up to 24 months

Arm 2) MEDI4736- 750 mg every 2 weeks. The drug will be restarted 14 days after surgery once the surgical wound has healed and then every 2 weeks after surgery. If there is no progression of disease, they will continue on treatment for up to 24 months

Arm 3) In the combination arm, 14 days after surgery, the drugs will be administered as follows: Tremelimumab will be administered IV every 4 weeks (Day 1 of each cycle) and MEDI4736 750mg every 2 weeks (Day 1 and Day 15 of each cycle) until the patients have received 7 doses of Tremelimumab and 14 doses of MEDI4736. Thereafter, from Cycle 7 (Week 25), Tremelimumab will be given every 12 weeks (+/-7 days) and MEDI4736 will be given every 2 weeks (+/- 2 days) until permanent discontinuation criteria (e.g. disease progression) is met. If there is no progression of disease, they will continue on treatment for up to 24 months.

(Note: This change to a 12 week regimen for tremelimubab after the first 6 doses is based on the current IB specifications and recent trial data).

Please refer to current Tremelimumab and Durvalumab IBs for more details

## 1.5 Rationale for the Current Study

The preclinical activity in glioma and the data in other solid tumors suggest that checkpoint inhibitors may be beneficial in GBM and should be evaluated especially since there is a high degree of PD-L1 seen in GBM. However, to further understand the effects of a cancer immunology approach in tumors, a pre-treatment trial to assess the immunologic changes in tumors prior to surgery would be important in understanding the effect of treatment.

This trial will assess the effect of each agent alone and then in combination.

## 1.5.1 Exploratory Studies

For patients who progress on trial and remain surgical candidates, tissue post treatment with Tremelimumab or MEDI4736 or the combination will be analyzed and compared to the prior specimen.

Additional exploratory studies will include assessment of:

- 1) Profile peripheral blood lymphocytes (PBL)
- 2) Tumor-infiltrating lymphocytes (TIL) throughout treatment.

3) Serum for tryptophan and downstream catabolites, as well as for cytokines.

## 2.0 OBJECTIVES & ENDPOINTS

## 2.1 Primary Objective & Endpoints

To determine the T-cell changes that occur in recurrent GBM treated with Tremelimumab and MEDI4736 as single agents and in combination. The changes from baseline will be assessed in blood samples and tissue samples before treatment and post-surgery for all patients in the 3 arms. A comparison between the changes observed in the 3 arms will be made.

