# 4.3 Supportive Care Guidelines & Concomitant Medications/Restrictions on Study

#### 4.3.1 Supportive Care

All medications used by patients during the study, with the reasons for use, will be recorded in the medical record and documented in the appropriate eCRF. For all subsequent visits, all concomitant therapy that is continuing or has been added, discontinued, or had a dosage change since the previous visit must be recorded in the medical record/eCRF as well.

• Antiemetic therapy may be used as needed and will be recorded in the medical record; 5HT antagonists are recommended.

- Hematopoietic growth factors (G-CSF) may be used per American Society of Clinical Oncology (ASCO) guidelines after cycle one.
- Corticosteroids should be used in the smallest dose to control symptoms of cerebral edema and mass effect, and should be discontinued if possible. Please confirm appropriate use with the PI.
- Febrile neutropenia may be managed according to the institution's infectious disease/ASCO guidelines. Measures may include appropriate laboratory testing, including blood and urine cultures and the initiation of broad-spectrum antibiotics. If a source for the fever is not identified or the fever resolves when the neutrophil count recovers, antibiotics may be discontinued and the patient observed. In this case growth factors may be used.
- If neurosurgical intervention is required for indications not related to tumor progression, these procedures must be documented, including the indications for surgery, surgical operative note, and pathology report.

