# 6.0 ENDPOINT ASSESSMENT

## 6.1 **Primary Endpoint**

To determine the T-cell changes (immunologic changes) that occur in recurrent GBM treated with Tremelimumab and MEDI4736 as single agents and in combination. The changes from baseline will be assessed in blood samples and tissue samples before treatment and post-surgery for all patients in the 3 arms. A comparison between the changes observed in the 3 arms will be made.

Only patients who have had pre-treatment blood sampling, have undergone surgery with pre-surgical blood sampling, and are able to continue to post-operative drug treatment with blood sampling prior to the first post-surgical dose will be evaluable for this endpoint.

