PBLs obtained prior to drug administration will be studied by flow cytometry to identify relative populations of CD8 T cells (CD3+, CD8+, PD1+/-), CD4 T cells (CD3+, CD8+, PD1+/-), regulatory T cells (CD4+, CD25+, FoxP3+), and suppressive monocytes (CD45+, CD11b+, PD-L1+). Repeat assessment of PBL markers will be determined by flow cytometry of subsequent samples taken on the day of surgery, post operatively (C1D1) and then on MRI days. Additionally, TILs extracted from patient tissue will be evaluated for relative populations of activated CD8 T cells (CD3+, CD8+, IFN-g+, PD1+/-), activated CD4 T cells (CD3+, CD8+, IFN-g+, PD1+/-), regulatory T cells (CD4+, CD25+, FoxP3+), and suppressive monocytes (CD45+, CD11b+, CD163+, PD-L1+). CTLA-4 expression on effector and regulatory T cells can also be measured by flow cytometry. Double-labeled tissue immunofluorescence can also be performed on FFPE sections to obtain immune effector cell counts, reported as # cells / 10 hpf. Optimized labeling schemes include: CD8/IFN-g, CD4/IFN-g, CD8/PD-1, CD4/PD-1, CD68/PD-L1, GFAP/PD-L1 (to identify PD-L1+ tumor cells).

We will use our stimulation protocol for IFN-g from PBL to look for increased peripheral T cell reactivity before and after drug treatment

Banked PBLs, TILs and FFPE tissue from prior patients treated without the study drug will serve as comparative controls.

*NOTE:* Any leftover tissue from the study patients will be banked for future use. This should be clearly stated in the consent form.

Please refer to laboratory manual for further details on collection, labeling, shipping, processing and storage.

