#### 10.3 Sample Size, Accrual and Data Analyses Plans

There will be three groups of patients, one group on each agent alone and one group treated with the combination agent. There will be 10 patients per group for a total of 30 patients. These 30 patients must be evaluable for the primary endpoint, meaning that they must have undergone surgery and their blood and tissue samples are available at both the pre- and post-surgery times. In order to attain 10 evaluable patients in each arm, a total of 45 patients will be accrued to the study. Sample sizes of 10 per group allow for the estimation of the proportion of responders in evaluable patients to be within 31% of its true value with 95% confidence. Mean change will be compared between arms. Using standard deviations of change, a sample size of 10 per group will allow the detection of differences of 1.25 standard deviations between groups with 80% power assuming a two-tailed test and a Type I error rate of 5%.

Immunologic measures will be summarized over the three or more time points (pre-treatment, following first treatment/pre-surgery, post-surgery) and changes in these measures will be assessed using repeated measures analysis of variance or Cochran's Q, followed by the paired t-test or the signed rank test for pairwise comparisons using Bonferroni corrections. Safety of the agents alone or in combination will be assessed by summarizing the frequency of adverse events by type, timing, grade and attribution. Response criteria will be based on RANO (including upcoming Immunologic RANO criteria) but since all patients will be post-surgery, the degree, if any, of

residual disease will vary. A patient is evaluable for efficacy if they have undergone at least one follow-up MRI after adjuvant therapy. Immunologic changes will be correlated with MRIs in a descriptive fashion. The secondary endpoint of progression-free survival as well as overall survival will be analyzed using Kaplan-Meier curves. Immunologic changes of T-cells and PDL1 levels will be correlated to survival outcomes using Cox regression analysis. MRI changes will be summarized using means or proportions and statistically analyzed using the signed rank test.

**Performance Status:** Patients will be graded according to Karnofsky Performance Status (KPS)(see appendix C).

**Evaluation of toxicity.** All patients will be evaluable for toxicity from the time of their first treatment as per NCI CTCAE version 4.03

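### The primary blood endpoint spans the craniotomy, so a within-arm change cannot be attributed to the drug; the on-drug pre-surgery sample is already drawn but not named as the primary contrast.

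*Combined protocol and SAP*

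**What the plan says.** Sections 2.1 and 6.1 set the primary endpoint as the change in T-cell measures in blood and tissue: "The changes from baseline will be assessed in blood samples and tissue samples before treatment and post-surgery for all patients in the 3 arms". Both add a between-arm element: "A comparison between the changes observed in the 3 arms will be made".

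Research blood is scheduled at the first pre-operative dose, on the day of surgery, at C1D1 and at each imaging visit (Section 5.1 note 8, Section 5.2 note 9, Section 9.1). C1D1 falls about 14 (±7) days after surgery (Section 5.2 note 2). Besides pre-treatment blood, Section 6.1 counts as evaluable only patients who "have undergone surgery with pre-surgical blood sampling, and are able to continue to post-operative drug treatment with blood sampling prior to the first post-surgical dose".

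Section 10.3 states: "Immunologic measures will be summarized over the three or more time points (pre-treatment, following first treatment/pre-surgery, post-surgery". Changes are tested by repeated measures ANOVA or Cochran's Q, then by Bonferroni-corrected pairwise tests. No pair is named as primary.

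All three arms receive study drug and then resection with standard post-operative care (Section 4.1). On steroids, Section 4.3.1 says: "Corticosteroids should be used in the smallest dose to control symptoms of cerebral edema and mass effect, and should be discontinued if possible". The only drug-free comparison is in Section 9.1: "Banked PBLs, TILs and FFPE tissue from prior patients treated without the study drug will serve as comparative controls".

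**The concern.** Between the pre-treatment draw and C1D1 every patient has had one dose of study drug (two drugs in Arm 3), a craniotomy with anaesthesia, and whatever corticosteroid was needed. The first part of the primary objective is descriptive and within-arm: what T-cell changes occur under each regimen. The contrast named in Sections 2.1 and 6.1 cannot separate the regimen from the operation.

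Two errors are possible. A change caused by surgery or steroids may be read as pharmacodynamic activity, or a real drug effect may be offset and missed.

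A sample less exposed to this problem is already taken. Day-of-surgery blood follows the drug and, if drawn early enough that day, precedes the operation. Section 10.3 analyses it, but as one of several time points, while Sections 2.1 and 6.1 point to the contrast that crosses surgery.

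**Working it through.** **1. The plan's own figures (Section 10.3).** Inputs: 10 per arm, difference 1.25 SD of change, two-sided alpha 0.05.

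- Normal approximation: power = Φ(1.25 × √(10/2) − 1.960) = Φ(2.795 − 1.960) = Φ(0.835) = 0.798, which matches the stated 80%. The exact two-sample t-test (18 df) gives 0.753.
- Precision of a proportion: 1.96 × √(0.25/10) = 0.310, which matches the stated 31%.

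The powered comparison is between arms and is expressed in SDs of change. Moving the second sample from C1D1 to the day of surgery leaves these figures as they are.

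**2. What each draw contains (Sections 4.2, 5.1, 5.2, 6.1).**

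| Draw | Approximate day from first dose | Doses before draw | Craniotomy before draw |
|---|---|---|---|
| First pre-operative dose | 0 | 0 | no |
| Day of surgery | 14 | 1 | no, if drawn before incision |
| C1D1 | 14 + 14 = 28 | 1 (drawn before the second) | yes |

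Both post-baseline draws follow the same single administration. The later one adds time, surgery and any steroid course, but no further drug. Section 4.1 itself expects two weeks to be long enough for immunologic change in the tumour.

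**3. Within-arm test when the drug does nothing.** The documents give no size for a surgery/steroid effect, so a shift of s SDs of change is assumed, equal in all arms. The paired t-test has n = 10, 9 df and noncentrality s × √10. The critical value is 2.262 at alpha 0.05, and 2.933 at 0.05/3 = 0.0167 (Bonferroni, three pairs of time points).

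| s | s × √10 | Significant at 0.05 | Significant with Bonferroni |
|---|---|---|---|
| 0 | 0 | 5.0% | 1.7% |
| 0.25 | 0.79 | 10.9% | 4.4% |
| 0.5 | 1.58 | 29.3% | 14.6% |
| 0.75 | 2.37 | 56.2% | 34.8% |
| 1.0 | 3.16 | 80.3% | 60.4% |

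The same table covers masking. A true drug effect of 1.0 SD, which this test detects with 80% power, leaves a net change of 1.0 − 0.5 = 0.5 SD if surgery and steroids pull the other way by 0.5 SD. Power is then 29%.

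**4. Between-arm test under the same shift.** A shift common to two arms cancels in their difference. Simulated rejection rates with no drug effect are 4.9%, 5.0% and 5.0% for s = 0, 0.5 and 1.0.

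**5. Tissue.** Study tissue is removed at the resection (Section 9.1) and the pre-treatment tissue is archival (Section 5.1 note 7). Recovery from this craniotomy cannot affect that comparison. Elapsed time and intervening therapy can, which is a separate matter.

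**The case against.** The strongest reply is that the plan already handles most of this. Pre-surgical blood is a condition of evaluability and an analysed time point, so pre-treatment versus pre-surgery is already one of the planned pairs, and a reader will see whether a change came before or after the operation. The only comparison with a stated power is the randomised one, where surgery is common to all arms. Much of this stands: the sample is neither missing nor ignored, and the between-arm test is sound unless steroid use after randomisation differs by arm. What remains is that Section 10.3 ranks no pair first, while Sections 2.1 and 6.1 name the one that crosses surgery.

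Four stronger readings are tempting and are not supported:

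- **That no drug-free comparison exists.** Section 9.1 names banked controls. It omits their number, disease stage, prior treatment, steroid status, sampling time and analysis. Comparability is therefore unknown, which does not show that it is absent.
- **That the plan contradicts its own rationale.** Section 1.5 says that "a pre-treatment trial to assess the immunologic changes in tumors prior to surgery would be important in understanding the effect of treatment". That sentence concerns tumour, and the resection specimen answers it.
- **That a peri-operative steroid course is built in.** No section describes one. Steroids are permitted, up to 8 mg a day at entry (Section 3.1.9), so they can also affect the pre-operative draw.
- **That the change would raise between-arm power.** If 10% to 30% of the variance of change were peri-operative, removing it would lift t-test power from 75% to between 80% and 89%. Those shares appear nowhere in the documents, and the calculation assumes the same raw difference at 14 days as at 28.

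**Conclusion.** The concern holds for within-arm changes in blood, and only there. As Sections 2.1 and 6.1 stand, such a change from pre-treatment to C1D1 cannot be attributed to the drug rather than to surgery or steroid use. There is no concurrent drug-free arm to resolve the ambiguity.

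The documents do not allow its size to be estimated. The range of 11% to 80% of arms (4% to 60% with Bonferroni) is an illustration that rests on an assumed shift of 0.25 to 1.0 SD and no drug effect. The randomised between-arm test stays near 5% provided the shift is equal across arms.

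A pre-operative contrast would not make a within-arm change purely pharmacological. Change over two weeks of disease and any steroid adjustment before surgery would remain. It removes the operation, the largest avoidable difference between the two samples. The change is worth making because it needs no new data.

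**What to change.** - **Sections 2.1, 6.1 and 10.3:** name pre-treatment to day-of-surgery blood as the primary blood contrast, within and between arms, and state that this draw is taken before anaesthesia and incision. Section 5.1 now says only day of surgery. Keep archival versus resection tissue as the tissue contrast.
- **C1D1 and later blood:** report as secondary, labelled as drug plus surgery.
- **Evaluability (Sections 6.1 and 10.3):** for the primary blood contrast, require the pre-treatment and pre-surgery samples only, so that patients who do not reach C1D1 are not excluded. The two sections should then use the same definition.
- **Steroids:** use the doses already recorded as concomitant medication (Section 4.3.1) to describe exposure at each draw.
- **Section 9.1:** limit the banked controls to recurrent glioblastoma after radiotherapy and temozolomide where available, and report the comparison as descriptive.

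Cost: revised wording and a fixed time for one existing draw. The sample size is unchanged. The primary blood read-out moves to about 14 days after the first dose instead of about 28, and fewer banked controls will qualify.

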## 2.2 Secondary Objectives & Endpoints

- 2.2.1 To evaluate the safety of either Tremelimumab or MEDI4736 alone and in combination in patients with recurrent GBM. The endpoints will be the number, frequency, and severity of adverse events (as defined by the NCI Common Terminology Criteria for Adverse Events or CTCAE version 4.03).
- 2.2.2 To determine post-surgery, the time to progression(per Modified RANO criteria and iRANO criteria see below) for patients treated with either Tremelimumab or MEDI4736 alone and in combination of both, This will be defined as the number of months from the time of first dose of study treatment until progression of disease or death by any cause.
- 2.2.3 To determine post-surgery the overall survival for patients treated with Tremelimumab or MEDI4736 alone and in combination of both. This will be defined as the number of months surviving from the time of first dose of study treatment until death by any cause.
- 2.2.4 To assess post-surgery, MRI changes in patients treated with either Tremelimumab or MEDI4736 alone and in combination of both.

## 2.3 Exploratory Objectives & Endpoints

2.3.1 To correlate T-cell changes and PDL1 expression with patient outcomes.

## **3.0 PATIENT ELIGIBILITY**

The target population for this study is patients with recurrent glioblastoma. This will be a single-center trial conducted at neuro-oncology clinic of Northwestern University.

A total of 30 evaluable subjects will be needed for this trial. The accrual cap is 45 patients, in order to cover those patients that do not make it to the first evaluable time point. Hence, the total accrual per arm will be up to 15. Approximately 4 potentially eligible patients are seen per month, and it is anticipated that at least 2 per month will be accrued. Potential patients may be referred to the Principal Investigator (PI) at Northwestern University, [name], at [contact].

Eligibility will be evaluated by the study team according to the following criteria. Eligibility waivers are not permitted. Subjects must meet all of the inclusion and none of the exclusion criteria to be registered to the study. Study treatment may not begin until a subject is registered.

